The study comprises two linked, complementary randomized trials. Trial 1, a large pragmatic trial, compares usual care with the clinician-facing Jumpstart for hospitalized older adults with serious illness (target n=2000; ADRD subset, target n=400). Trial 2, a comparative effectiveness trial is a three-arm trial that compares the clinician-facing Jumpstart, the bi-directional, patient-specific Jumpstart and usual care (n=600). Subjects are enrolled from the UW Medicine hospitals (Harborview Medical Center, UW Medical Center - Montlake, UW Medical Center – Northwest). For Trial 1, eligible patients are ≥ 55 years, admitted for a minimum of 12 and a maximum of 96 hours prior to study enrollment to inpatient services, without a documented GOCD during admission, and meet criteria for serious illness; hospitalized patients >80 years are also eligible. For Trial 2, eligible patients meet the same criteria and, in addition, must be sufficiently fluent in English to complete questionnaires and not be under COVID precautions to allow in-person recruitment. For Trial 2, eligible family may include any of the following: legal guardians, durable power of attorney for healthcare, spouses, adult children, parents, siblings, domestic partners, other relatives, and friends. In addition, we will conduct qualitative interviews with key stakeholders including patients/families (n=40, subgroup of patients enrolled for Trial 2) and clinicians (n=50 across Trial 1 and Trial 2).

2) Specific Aims:

Specific Aim 1 (Trial 1): Evaluate the effectiveness of a novel clinician-facing Jumpstart, compared with usual care, for improving the quality of care; the primary outcome is EHR documentation of a goals-of-care discussion during the 30 days after enrollment. Secondary outcomes focus on intensity of care: ICU use, ICU and hospital free days, costs of care during the hospitalization, and 7- and 30-day hospital readmission.

Specific Aim 2 (Trial 2): Evaluate the efficacy of the bi-directional, patient-specific Jumpstart compared to the clinician-facing Jumpstart and usual care for improving quality of care; the primary outcome is EHR documentation of a goals-of-care discussion 30 days after enrollment. Secondary outcomes include: intensity of care outcomes from Aim 1 and patient- and family-reported outcomes assessed by surveys at 3-5 days and

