e) Sampling patients with ADRD

Given the dramatically increasing prevalence of ADRD in the US and the rising intensity of care among these patients,^{11,13} it is particularly important that we understand the effect of interventions to improve quality of palliative care in this group. We designed both trials to be powered to examine heterogeneity of treatment effects (HTE) in this important group. For Trial 1, we will plan to continue recruitment to enhance power in this subgroup. For Trial 2, we will prioritize recruitment of patients with ADRD to maximize this subgroup sample size. We hypothesize that the interventions will be equally effective in this population, but that the proportion of patients with decisional capacity will be lower (enrolling more family members). However, we believe it is important to explicitly examine this hypothesis given the unique features of intensity of care at the end of life for this important and increasing population.

f) Randomization

Patients are randomized in a 1:1 ratio in Trial 1 and 1:1:1 ratio in Trial 2 using variable size blocks and stratified for hospital and ADRD vs. no ADRD. Participating family members or legal surrogate decision makers are assigned to the same arm as the corresponding patient.

g) Intervention

Clinician-facing Jumpstart: First, we use automated methods to examine inpatient and outpatient EHR notes prior to the current admission, identifying current code status as well as all prior POLST forms and advance directives; this information is included on Jumpstart Guides to inform discussions. Second, we deliver the Jumpstart Guide to the primary hospital team (all attending and resident physicians and advanced practice providers) via secure email and either a page (Trial 1) or Epic SecureChat message (Trial 2) alerting the physicians to the presence of the Jumpstart Guide in their email, with the addition of in-person delivery of a paper version in Trial 2 only.

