Costs of care	Intensity of care/intervention costs	EHR: During hospital stay, 30 and 90 days post-randomization.
All-cause mortality at 90 days and 1 year	All-cause mortality	Washington State death certificates
Aim 2 outcomes (not used in Aim 1 since the Trial 1 is a pragmatic trial without contact with patients or family members)		
Patient/family-reported discussion of goals ^{9,25}	Goals-of-care discussion occurrence	Survey: 3-5 days & 4-6 weeks post-randomization

Quality of Communication (QOC) ^{24,26,28}	Quality of communication	Survey: 3-5 days post randomization
SUPPORT question ³¹	Goal-concordant care	Survey: 3-5 days & 4-6 weeks post-randomization
HADS – anxiety and depression ^{36,37}	Symptoms of anxiety & depression	Survey: 4-6 weeks post-randomization
EQ-5D-5L	Health-related QOL	Survey: 4-6 weeks post-randomization
Patient/family reported ED, hospitalization and outpatient utilization	Healthcare utilization	Survey: 4-6 weeks post-randomization
CollaboRATE ⁶⁰	Shared decision-making	Survey: 3-5 days post randomization

6) Analyses

We will follow the intention-to-treat principle for all analyses.

a) Primary Outcome (presence of goals of care discussion within 30 days after randomization)

The effect of intervention on the primary outcome will be quantified by the difference in proportions and evaluated with a linear regression model with robust standard errors. The predictor of interest is randomization arm (Clinician-facing Jumpstart or usual care for Trial 1; or Clinician-facing Jumpstart, Bi-directional Jumpstart, or usual care for Trial 2). The model will adjust for hospital site and ADRD status, since randomization is stratified on these factors. This model assumes the effect of intervention is the same for patients with and without ADRD. We will also include an interaction between randomization arm and ADRD, which allows the effect of intervention to vary by ADRD status and allows evaluation of the effect among those with and without ADRD. We will evaluate the timing of goals-of-care discussions with a Cox proportional hazards model.

b) Additional Outcomes

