Trial 1: With a total sample size of 2000 (1000 per group), two-sided significance level (α) of 0.05, and a variance estimate based on the proportion in the control group only, we have 80% power to detect a difference in proportions between those randomized to Clinician-facing Jumpstart and usual care of at least 0.06. We assumed a proportion in the control group of 0.54 based on preliminary data. If the total number of patients with ADRD in Trial 1 is 400 (200 per group), we would have 80% power with $\alpha=0.05$ to detect a difference in proportions of 0.14 among those with ADRD.

Trial 2: With a total sample size of 600 (200 per Clinician-facing Jumpstart, 200 per Bi-directional Jumpstart, and 200 per usual care), we have 80% power to detect a difference in proportions of 16% for each of the 3 pairwise comparisons assuming an overall $\alpha=0.05$ and a Bonferroni adjustment for the 3 comparisons ($\alpha=0.017$ for each comparison) and variance based on a proportion of 0.54.

b) Sample size for qualitative analyses

For Aim 3 qualitative analyses, it is important to achieve theoretical saturation (no new themes emerging).^{64,66} Based on our prior studies, we anticipate achieving saturation by 80 interviews for understanding patients/families and clinician perspectives.^{16,46,54-59} We will monitor for saturation and will recruit additional participants if needed.

8) Data management and quality control to achieve scientific rigor

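### Protocol 4e says both trials are powered for heterogeneity of effect by ADRD; Trial 2's design does not deliver this at any ADRD share, and Trial 1's printed figure is for the effect within ADRD

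*Protocol*

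**What the plan says.** Protocol 4e (Sampling patients with ADRD) makes a statement about design: "We designed both trials to be powered to examine heterogeneity of treatment effects (HTE) in this important group". It then sets out what is to be examined: "We hypothesize that the interventions will be equally effective in this population". On numbers, 4e says that Trial 1 recruitment will continue in order to add power in this subgroup. For the other trial it says only: "For Trial 2, we will prioritize recruitment of patients with ADRD to maximize this subgroup sample size". Section 10a adds that the ADRD sample size is meant to allow the hypothesis to be tested on the primary outcome in each of the two trials.

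The analysis is in Protocol 6a: "We will also include an interaction between randomization arm and ADRD, which allows the effect of intervention to vary by ADRD status". The SAP repeats the interaction for all outcomes under Additional analyses. Its arm variable has two levels (control, intervention), so it reads as a Trial 1 document.

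The overview gives Trial 1 an ADRD target, "target n=2000; ADRD subset, target n=400", and gives Trial 2 only its total of 600. Section 7a states that Trial 1, with 200 ADRD patients per group, has 80% power "to detect a difference in proportions of 0.14 among those with ADRD". For Trial 2 it gives one figure, for all patients: "we have 80% power to detect a difference in proportions of 16% for each of the 3 pairwise comparisons", at 0.017 per comparison.

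**The concern.** Heterogeneity of treatment effect means that the effect differs between ADRD and non-ADRD patients. The planned analysis of that is the interaction. An interaction is estimated much less precisely than a main effect, so power for a main effect, or for the effect inside one subgroup, does not carry over to it.

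Section 4e claims the power property for both trials. No interaction size is named for either, and the text contains no ADRD calculation for Trial 2.

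The direction of the hypothesis makes this matter. The investigators expect no difference, so low power favours the result they expect. If the Trial 2 interaction is non-significant and the protocol describes the trial as powered for it, readers may conclude that the intervention works equally well in ADRD when the data could not have shown otherwise.

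**Working it through.** **Inputs.** From Protocol 7a: control proportion 0.54; variance taken from the control proportion only, so v = 0.54 × 0.46 = 0.2484; two-sided alpha 0.05 (Trial 1) and 0.017 per pairwise comparison (Trial 2); 80% power; 1000 per arm in Trial 1, of whom 200 have ADRD (so 800 do not); 200 per arm in Trial 2. The Trial 2 ADRD share is not given in the text, so it is varied. The multipliers are 1.960 + 0.842 = 2.802 at alpha 0.05 and 2.387 + 0.842 = 3.228 at 0.017.

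**Step 1: the protocol's own figures.** Detectable difference = multiplier × √(2v/n per arm).

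- Trial 1 overall: 2.802 × √(0.4968/1000) = 0.062 (printed 0.06).
- Trial 1 within ADRD: 2.802 × √(0.4968/200) = 0.140 (printed 0.14).
- Trial 2 pairwise: 3.228 × √(0.4968/200) = 0.161 (printed 16%).

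All three reproduce, allowing for rounding.

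**Step 2: Trial 1 interaction.** SE = √(2v(1/200 + 1/800)) = 0.0557. The detectable interaction is 2.802 × 0.0557 = 0.156, and the 95% CI half-width is 1.960 × 0.0557 = 0.109. Power for an interaction of 0.14 is Φ(0.14/0.0557 − 1.960) = 71%. For an interaction of 0.06 it is 19%.

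**Step 3: Trial 2, pairwise.** With k ADRD patients per arm, the interaction SE is √(2v(1/k + 1/(200 − k))). The within-ADRD SE is √(2v/k).

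| ADRD share | Interaction, alpha 0.05 | Interaction, alpha 0.017 | Within ADRD, alpha 0.05 |
|---|---|---|---|
| 20% | 0.349 | 0.402 | 0.312 |
| 30% | 0.305 | 0.351 | 0.255 |
| 40% | 0.285 | 0.328 | 0.221 |
| 50% | 0.279 | 0.322 | 0.197 |
| 60% | 0.285 | 0.328 | 0.180 |
| 80% | 0.349 | 0.402 | 0.156 |

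The interaction is best at 50%, where SE = √(0.4968 × 2/100) = 0.0997 and the 95% CI half-width is 0.195.

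**Step 4: power at a yardstick.** The documents name no interaction size. Trial 2's own overall detectable difference, 0.16, corresponds to the full target effect in one group and none in the other. At 50% ADRD, power is Φ(0.16/0.0997 − 1.960) = 36% at alpha 0.05 and 22% at 0.017. Reaching 80% at alpha 0.05 would need 8v × (2.802/0.16)² ≈ 610 per arm, about three times the planned 200, even at 50% ADRD.

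**Step 5: other variance assumptions.** Section 6a uses robust standard errors, so cell-specific variances are also relevant.

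- If the effect is confined to one group (0.54 rising to 0.70 there, 0.54 in the other cells), power at 0.16 is 37%.
- On the same pattern, 80% power is reached at about 0.27.
- Across a wider set of assumed effects, the detectable interaction runs from about 0.24 to 0.28.
- Pooling both Jumpstart arms against usual care, which is not planned, gives 0.242 at alpha 0.05.

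**The case against.** The best counter-argument is that 4e means something narrower: enough ADRD patients to estimate the effect in that group. The wording there about subgroup size, the statement in 6a that the model also gives effects with and without ADRD, and the calculation in 7a all fit that reading. For Trial 1 it succeeds, because 0.14 is the right figure for it. For Trial 2 it does not. No ADRD target or figure appears in the text, and the within-ADRD detectable difference at alpha 0.05 would be about 0.20 at 50% ADRD and 0.31 at 20%, both above the trial's own 0.16. A Trial 2 target might stand in Figure 1, which is not shown. That would matter on this reading, but it cannot change the interaction result, which covers every share.

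It is also fair that section 7a sizes Trial 2 at 0.017, so a figure at 0.05 needs its alpha stated; that the three-arm model in 6a does not specify pairwise interaction tests; and that the SAP places the interaction among additional analyses.

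Several stronger readings are tempting but not supported:

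- *That 0.28 is an absolute floor, or that the Trial 2 test must miss a 0.16 interaction by some fixed minimum rate.* Both depend on a variance of 0.54 × 0.46 in every cell. Other assumptions move them, though not near 80% power at 0.16.
- *That Trial 1's subgroup calculation is wrong.* It is correct for what it describes. Quoting only the 19% power at 0.06 would overstate the gap, since power is 71% at 0.14.
- *That Trial 2 should match Trial 1's 0.14 within ADRD.* Nothing in the protocol requires this.
- *That the plan intends to treat a null interaction as equality.* No passage says so. The wording invites that reading but does not state it.

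**Conclusion.** The power statement in 4e is wrong as written for Trial 2 and too broad for Trial 1. If heterogeneity means a difference in effect, Trial 2 does not have the stated property at any ADRD share: the best case is an interaction of about 0.28 at alpha 0.05 (0.32 at 0.017), far above the 0.16 that the trial is sized for overall. If it means the effect within ADRD, the text gives nothing to support the claim for Trial 2. The Trial 1 shortfall is modest, and disappears on the within-ADRD reading.

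This rests on the protocol's control proportion and variance convention, equal arms, and one pairwise contrast. The yardstick of 0.16 is borrowed from the protocol's overall calculation. The conclusion holds under the alternative variances tried. The planned models are sound; the fault is in the property claimed for them. It should be corrected, but it does not threaten the primary analysis of either trial.

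**What to change.** - **Protocol 4e:** limit the power statement to Trial 1's within-ADRD difference of 0.14 (200 per group) and remove the heterogeneity power claim for Trial 2. The sentence on prioritising ADRD recruitment can stay.
- **Protocol 10a:** refer to Trial 1 only, or print the Trial 2 ADRD target with its within-ADRD detectable difference.
- **Protocol 7a, if interaction figures are added:** state the assumptions with them. For example: assuming a variance based on 0.54 in all cells and 80% power, the detectable arm-by-ADRD interaction is 0.156 in Trial 1 (400 of 2000 with ADRD, two-sided alpha 0.05); in Trial 2 it is at best about 0.28 at alpha 0.05, or about 0.32 at 0.017, for a pairwise comparison with half the patients having ADRD.
- **Protocol 6a, and the SAP for Trial 1:** report the ADRD-specific effects and the interaction as estimates with 95% confidence intervals, and say that a non-significant interaction will not be taken as evidence of equal effectiveness.

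The cost is wording only; design, enrolment and models are unchanged. The stated power becomes less favourable, and a null interaction can no longer be cited as support for equal effectiveness. The SAP already refers to EHR data pulled for analysis, so in the Trial 1 report the observed interval will supersede the design figure.

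### Trial 1's stated 80% power for a difference of at least 0.06 is slightly too favourable through rounding: the plan's own inputs give 0.0624 at 80% power, and about 77% power at 0.06

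*Protocol*

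**What the plan says.** Protocol section 7a (Sample size considerations for the primary outcome) takes the Trial 1 sample size as given, "With a total sample size of 2000 (1000 per group", and reports what it can detect. The other inputs are a "two-sided significance level (α) of 0.05" and "a variance estimate based on the proportion in the control group only". The control proportion is also stated: "We assumed a proportion in the control group of 0.54 based on preliminary data". From these the section concludes that "we have 80% power to detect a difference in proportions between those randomized to Clinician-facing Jumpstart and usual care of at least 0.06".

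The same section gives two further detectable differences at 80% power: 0.14 for the ADRD subset of Trial 1 (200 per group), and 16% for each pairwise comparison in Trial 2 (200 per arm, alpha 0.017). All three are given to two decimals or a whole percentage.

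Section 4f confirms equal allocation: "Patients are randomized in a 1:1 ratio in Trial 1". Under section 6a the primary outcome is compared as a difference in proportions, "evaluated with a linear regression model with robust standard errors", adjusted for hospital site and ADRD status.

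**The concern.** The Trial 1 sentence supplies everything needed to check it, and the check does not return 80% at 0.06. The wording makes 0.06 a lower limit, so every difference from 0.06 up to 0.0624 falls inside the claim while having less than 80% power.

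What is at stake is how the power statement is read later. It is the main one for the primary comparison of the larger trial. If Trial 1 shows no clear effect, readers may judge that result against 80% power for 6 percentage points, which is a little more than the design has on its own assumptions. No estimate, test or enrolment figure depends on it.

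**Working it through.** **Inputs (protocol section 7a; allocation also in section 4f)**
- n = 1000 per group, 1:1
- two-sided alpha 0.05, so z = 1.960
- 80% power, so z = 0.842
- control proportion 0.54, with its variance applied to both groups: 0.54 × 0.46 = 0.2484

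**1. The plan's figure**
- SE = √(2 × 0.2484 / 1000) = 0.02229
- Difference detectable with 80% power = (1.960 + 0.842) × 0.02229 = 0.0624

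To two decimals this is 0.06, so the printed figure is recovered as a rounded value.

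**2. Power at exactly 0.06**
- 0.06 / 0.02229 − 1.960 = 0.732
- Φ(0.732) = 0.768, that is 76.8% power and a type II error of 23.2%

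**3. Does another standard method restore 80%?**

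| Method (1000 per group, difference 0.06) | Power |
|---|---|
| Control-only variance (the plan's) | 76.8% |
| Separate variances, 0.54 and 0.60 | 77.5% |
| Pooled variance under the null, 0.54 vs 0.60 | 77.4% |
| Pooled variance under the null, 0.54 vs 0.48 | 76.6% |
| Arcsine transformation, 0.54 vs 0.60 | 77.4% |

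No two-sided method comes within 2 points of 80%. A one-sided test at 0.05 gives 85.2% but contradicts the stated two-sided level. Counting the variance of one group only gives 96.8%, but that is not the variance of a difference between two groups.

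**4. The section's other figures, by the same formula**

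| Comparison | Computed difference | Printed | Power at printed value |
|---|---|---|---|
| Trial 1, all patients | 0.0624 | 0.06 | 76.8% |
| Trial 1, ADRD (200 per group, alpha 0.05) | 0.1396 | 0.14 | 80.2% |
| Trial 2 (200 per arm, alpha 0.05/3) | 0.161 | 16% | 79.3% |

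One formula with ordinary rounding explains all three. Rounding removes 0.0024 from 0.0624, about 4% of it. For the other two figures the relative change is under 1%, so power barely moves.

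**5. For reference only**
- n per group for 80% power at exactly 0.06 = 2 × 0.2484 × (2.802)² / 0.06² = 1083.1 to 1083.2, depending on rounding of the z values; rounded up, 1084.
- With n fixed at 1000, covariate adjustment would have to explain 1 − (0.06 / 0.06244)² = 7.7% of the outcome variance to bring power at 0.06 up to 80%.

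**The case against.** The strongest reply is that nothing was miscalculated: 0.0624 correctly rounds to 0.06, and it is unfair to treat a two-decimal figure as exact and then solve back for power. The point about cause stands. It does not rescue the sentence, because a detectable difference worded as a minimum should not be rounded down, and on a difference this small two decimals cost about 3 points of power.

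A second reply is that the design does not rest on 0.06. This also stands. The section starts from a fixed 2000 and reports what it can detect; neither document calls 0.06 a minimum important difference or uses it as a decision threshold. A null result should in any case be read from the estimated difference and its uncertainty.

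A third reply is that planned adjustment for site and ADRD, and the intention in section 4e to continue Trial 1 recruitment for the ADRD subgroup, could raise power. Both are possible, but neither is quantified and section 7a claims no gain from either.

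A reader might go further and infer that Trial 1 is under-enrolled by about 8% (1084 against 1000 per group). The documents do not support that, since they never set 80% power at exactly 0.06 as a requirement from which n was derived. Nor do they support an inference of selective rounding: the ADRD figure was rounded up, against the plan's interest.

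**Conclusion.** The concern holds as a minor error of statement caused by rounding. On the plan's own inputs, Trial 1 has 80% power for a difference of 0.0624, not 0.06. Power at 0.06 is 76.8%, or 77.5% with separate variances. The gap is 0.0024 on the difference scale and about 3 points of power.

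This rests on the normal approximation, a control proportion of 0.54, 1000 analysed patients per group and no precision gain from covariates, which is how section 7a frames its own calculation. It is not evidence of a wrong formula or a design failure.

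**What to change.** Replace the Trial 1 sentence in protocol section 7a with wording such as: *With 1000 per group we have 80% power to detect a difference of about 0.0624 (6.2 percentage points), and about 77% power for 0.06.* Keep the stated inputs beside it.

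The cost is one sentence and a slightly less favourable headline figure. Enrolment, randomization, analysis and the other two power statements need no change.

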Use of the EHR to identify seriously ill, hospitalized patients without a goals-of-care discussion: Recent research agendas highlight the lack of research utilizing the EHR to implement interventions that improve serious illness communication.^{8,9} We will use a validated EHR-based quality metrics program to identify hospitalized patients over age 55 with chronic serious illness who do not have EHR documentation of a goals-of-care discussion. We have developed an innovative NLP/ML protocol to identify inpatient and outpatient documentation of goals-of-care discussions in any type of EHR note, including admission notes, progress notes, and discharge summaries (*see preliminary data*). In this way, we not only target a population likely to benefit from the intervention but also do so with methods that are generalizable and scalable.¹⁰⁵

Examine both a clinician-facing Jumpstart and a patient-specific Jumpstart in an innovative study design: The intervention is based on our recently completed trial in the outpatient setting of the patient-specific intervention (Jumpstart), which is an individualized communication-priming intervention, targeting both patients and clinicians and providing each with information obtained from patient surveys in order to guide a goals-of-care discussion.² This intervention is innovative because it is one of the few that involves clinicians as well as patients and family members (bi-directional). However, a question raised by reviewers of our prior trial² was whether the individualized survey-based component was necessary, especially given the resources needed to implement it. Therefore, we have developed this innovative study design that combines a large pragmatic trial of a clinician-facing Jumpstart compared to usual care (using a waiver of informed consent to facilitate enrollment and the pragmatic approach) and a smaller comparative effectiveness trial of a bi-directional, patient-specific Jumpstart that will include individual patient or surrogate consent for participation as well as completion of surveys to generate the patient-specific Jumpstart.

[figure not shown]

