Cost assessments for Aim 1 are limited to costs available in the UW Medicine EHR, and we will not be able to assess costs from other healthcare systems after hospital discharge. Most of the benefits we anticipate for this intervention will occur during the hospitalization, although there may be ongoing reductions in costs after hospitalization related to changes in the goals of care as a result of the intervention. We will evaluate for such effects in Trial 2, and the limitation of not having access to these costs from outside UW Medicine in Trial 1 is diminished somewhat because this is a randomized trial.

11) Anticipated findings

These interventions use the EHR to identify patients who should have documentation of a goals-of-care discussion but do not, and then prompt and guide such discussions with either: a) a clinician-facing prompt and guide for clinicians only, along with information about prior advance care planning completed prior to the hospitalization; or b) a bi-directional, patient-specific intervention that provides patient-specific support to clinicians, patients and family members. We anticipate that both interventions will be effective compared to the usual care arm, and that this study will provide important options for healthcare systems. Economic analyses will allow us to evaluate the effect on costs of care, after factoring in the costs of implementing these interventions, to enhance dissemination. If either or both of these interventions are not effective, the results

and the interviews in Aim 3 will provide important information to shape, direct and deliver future interventions.

References

4. Halpern SD. Toward Evidence-Based End-of-Life Care. *N Engl J Med* 2015;373:2001-3.
5. Halpern SD. Goal-Concordant Care - Searching for the Holy Grail. *N Engl J Med* 2019;381:1603-6.

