## General characteristics of analysis:

- The predictor of interest in all regression models will be the randomization group: 0=control, 1=intervention.
- Regression models will be automatically adjusted for hospital site and ADRD status (as defined at the time of randomization). There will be no other covariates in the models.
- For Cox models, we will use Stata's "exactp" method for correcting for ties unless there are problems with that method, in which case we will use the Efron method. (See page 4.)

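### Trial 2: a three-arm step-down rule, stated in Protocol 6a, would find more second and third differences than single-step Bonferroni at the same 5% family-wise error (optional improvement)

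*Protocol*

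**What the plan says.** Protocol section 7a (Trial 2) plans 600 patients, 200 per arm, and states that "we have 80% power to detect a difference in proportions of 16% for each of the 3 pairwise comparisons". It assumes overall α = 0.05, "a Bonferroni adjustment for the 3 comparisons" (0.017 each), and a variance based on a proportion of 0.54. One fixed threshold for every pair is single-step Bonferroni.

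Protocol section 6a says of the analysis that "The effect of intervention on the primary outcome will be quantified by the difference in proportions", using linear regression with robust standard errors adjusted for site and ADRD. It adds that "The predictor of interest is randomization arm", with three levels in Trial 2. It gives no global test, testing order or adjustment for the three comparisons.

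The supplied SAP codes two groups ("The predictor of interest in all regression models will be the randomization group: 0=control, 1=intervention") and appears to cover Trial 1 only. Its silence on three arms is therefore not held against the plan.

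**The concern.** Trial 2 is meant to yield more than one conclusion. Specific Aim 2 tests the bi-directional guide "compared to the clinician-facing Jumpstart and usual care for improving quality of care". Section 11 says "We anticipate that both interventions will be effective compared to the usual care arm". Section 3b (Innovation) gives the motive for comparing the two guides: "whether the individualized survey-based component was necessary, especially given the resources needed to implement it". Each of these needs a second or third rejection to be answered.

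Single-step Bonferroni holds every comparison at 0.05/3 whatever the other two show. With three arms that is stricter than 5% family-wise control requires. Once one difference is established, at most one true null can remain, and Bonferroni then spends only about 1.8% of the 5% allowed. The unspent error is lost power for the later comparisons.

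**Working it through.** **1. Reproduce the plan's figure.** Inputs from section 7a: n = 200 per arm, p = 0.54 for the variance, 80% power, α = 0.05/3. Two-sided testing is stated for Trial 1 and assumed for Trial 2.

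- SD = √(0.54 × 0.46) = 0.4984; standard error of a difference = 0.4984 × √(2/200) = 0.04984.
- Detectable difference = (z₁₋α/₂ + z₀.₈₀) × SE = (2.394 + 0.842) × 0.04984 = **0.161**, which matches the stated 16%.
- Power at exactly 0.16 = Φ(0.16/0.04984 − 2.394) = 0.793. At α = 0.05 it would be Φ(0.16/0.04984 − 1.960) = 0.894.

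**2. Why the step-down rule (Shaffer) is valid.** Test the smallest p-value at 0.05/3; if it is rejected, test the other two at 0.05.

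- All three nulls true: an error needs at least one p-value below 0.05/3, so its probability is at most 3 × 0.05/3 = 0.05.
- Any null false: at most one null is true. It is never tested above 0.05, so the error is at most 0.05.
- Every Bonferroni rejection has p < 0.05/3 and is kept.

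**3. Size of the gain.** 400,000 simulated trials per scenario, 200 per arm, unpooled Wald tests. Rates are usual care / clinician-facing / bi-directional. Only 0.54 and the 16-point difference come from the protocol; the other rates are assumed.

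| Rates | Quantity | Bonferroni | Step-down |
|---|---|---|---|
| 0.54/0.70/0.70 | both true differences found | 72% | 84% |
| 0.54/0.54/0.70 | both true differences found | 72% | 84% |
| 0.54/0.68/0.68 | both true differences found | 54% | 69% |
| 0.54/0.60/0.70 | bi-directional vs clinician-facing | 39% | 54% |
| 0.54/0.62/0.70 | bi-directional vs clinician-facing | 25% | 38% |
| 0.54/0.60/0.66 | bi-directional vs clinician-facing | 13% | 21% |
| 0.54/0.58/0.62 | bi-directional vs clinician-facing | 6% | 9% |

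**4. Limits of the gain.**

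- The chance of at least one rejection is the same under both rules: 93% (0.54/0.70/0.70), 85% (0.54/0.60/0.70), 57% (0.54/0.60/0.66) and 27% (0.54/0.58/0.62).
- The largest contrast barely moves: 82.5% to about 84% at 0.54/0.60/0.70.
- Finding all three differences stays unlikely at moderate effects: 1.4% to about 6.4% at 0.54/0.60/0.70.
- The 0.05 level applies only after a first rejection, so (1.960 + 0.842) × 0.04984 = 0.140 is not the new detectable difference. With two equal true effects of 14 points, power per comparison goes from 69% to 76.5%. It reaches 80% at about 14.5 points under step-down and about 15.6 under Bonferroni.

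**5. Error rates and intervals.**

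- Simulated family-wise error with all arms equal is just under 5% (4.7% to 4.9% across runs), identical under both rules. With one true null it is about 1.8% under Bonferroni and about 5% under step-down.
- At least one 98.3% interval includes zero for a step-down rejection in 1.3% of trials with all arms equal, 14.6% at 0.54/0.70/0.70, 24.4% at 0.54/0.60/0.70, 26.0% at 0.54/0.62/0.70 and about 8% at 0.54/0.58/0.62. Simultaneous coverage of these intervals stays at 95%.
- Unadjusted 95% intervals are not a remedy. Simultaneous coverage is about 88%, and in 4.5% to 17.2% of trials at least one excludes zero where the rule does not reject.

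**6. Check with the section 6a model.** Linear regression with robust standard errors, adjusted for site and ADRD, under assumed site and ADRD effects; 40,000 trials per scenario. Both true differences at 0.54/0.70/0.70: 74% to 86%. Guide versus guide at 0.54/0.60/0.70: 40% to 54%. Family-wise error: 4.6% under both rules with all arms equal; with one true null, 1.6–1.7% to 4.9%.

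**The case against.** The strongest reply is that nothing is wrong. Bonferroni is valid, section 7a names it for this outcome and these comparisons, and a reader would naturally carry it into the analysis. A separate Trial 2 SAP may also exist. That is fair, and it is why this is offered only as an option.

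Second, the added error can fall on the question that section 3b raises. If both guides work equally (0.54/0.70/0.70), the chance of falsely declaring them different rises from 1.8% to about 5%. That stays within the plan's own limit, but investigators could reasonably prefer the stricter protection. The mismatch between 98.3% intervals and some step-down decisions is likewise a real reporting cost, because section 6a makes the difference in proportions the effect measure.

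Third, the 72% to 84% gain needs 16-point effects, which the protocol gives as detectable, not expected. Clinician-facing versus usual care is also Trial 1's main question, with 2000 patients, though delivery and eligibility differ somewhat. Both points stand and temper the gain.

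Fourth, a global 2-df test at 0.05 followed by pairwise tests at 0.05 also controls the error for three arms, and it slightly raises the chance of any finding (92.9% to 93.9% at 0.54/0.70/0.70). It is a legitimate alternative, but it can lose a Bonferroni rejection. With equal variances and the third arm midway, a pair at z = 2.394 gives a global statistic of 2.394² = 5.73, below the 5% critical value of −2 ln 0.05 = 5.99.

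**Conclusion.** The point holds as an optional improvement; it is not an error in the plan. Section 7a's figure is correct. For three arms, step-down keeps every Bonferroni rejection and respects the same 5% family-wise limit. At the assumed rates it adds 12 to 15 percentage points to the chance of finding both true differences when two comparisons differ by 14 or 16 points. For guide versus guide it adds 3 to 15 points, depending on the rates. It does nothing for the first rejection, and it helps little when effects are small. The validity argument needs no assumption about rates; the size of the gain depends on rates in the two Jumpstart arms that the documents do not give.

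**What to change.** Before Trial 2 outcomes are compared by arm, add one rule to section 6a, for example:

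> Order the three pairwise p-values. Test the smallest at 0.05/3. If it is rejected, test each of the other two at 0.05; otherwise stop.

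- Keep 16% in section 7a as the conservative figure.
- Report adjusted p-values: three times the smallest p-value, capped at 1; for each of the others, the larger of that value and its own p-value.
- Report Bonferroni 98.3% simultaneous intervals, and state that one may include zero for a comparison rejected only at the second step. Do not substitute unadjusted 95% intervals.
- Disclose that the guide-versus-guide false-positive rate can rise from 1.8% to about 5% when both guides work equally.

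If the investigators prefer intervals that match every decision, or stricter protection on the guide-versus-guide question, section 7a's rule can be copied into section 6a instead (each comparison at 0.05/3, with 98.3% intervals). Either choice costs two or three sentences and no patients.
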